## 8.3. Adverse Events

All AEs will be recorded from the time of the first treatment through the end of the follow up period. Adverse events occurring for the first time, or worsening in severity, on or after the first dose of study drug or placebo will be considered to be TEAEs. Only TEAEs will be presented in summary tables, but all AEs will be listed with a flag indicating if the AE was treatment-emergent. Adverse events will be coded using the Medical Dictionary for Regulatory Activities (MedDRA) to identify the system organ class and preferred term. The MedDRA version used will be within 1 full version of the latest version at study end. Any ear-related AE, whether occurring in 1 or both ears, will only be counted once in subject incidence counts per system organ class and preferred term.

Treatment-emergent AEs will be summarized by treatment group and overall for all subjects in the SfAS. The summary will display the total number of TEAEs as well as the count and percentage of subjects experiencing any TEAE. The total number of TEAEs and the count and percentage of subjects experiencing at least 1 TEAE in each system organ class and preferred term will also be shown. All percentages will use the number of subjects in the SfAS by treatment group as the denominator. Therefore, if a subject has more than 1 AE within a system organ class, the subject will be counted only once in that system organ class. If a subject has more than 1 AE that codes to the same preferred term, the subject will be counted only once for that preferred term. The tabular summary will be sorted by descending frequency of system organ class and preferred term for overall incidence.

Treatment-emergent AEs will also be summarized by maximum relationship to study drug and maximum severity. Relationship to the drug will be scored as Related, Possible, Unlikely or Not Related. Related AEs will be classified as those scored as Related and Possible. Severity will be rated as Mild, Moderate, or Severe. All percentages will use the number of subjects in the SfAS by treatment group as the denominator. Summary tables will reflect a count and percentage of subjects experiencing at least 1 TEAE in each system organ class, preferred term and grouping, relationship, or severity. If a subject experiences more than 1 AE within system organ class or preferred term, that subject will be counted only once for that event under the maximum severity or most related category for the study drug. Similarly, in the event that relationship or severity data are missing, the study analysis will include a category for missing relationship or severity in the summary tables. The tabular summaries will be sorted by descending frequency of system organ class and preferred term based on the overall incidence.

For ear-related TEAE analyses where the ear is the unit of analysis, ears will be summarized according to whether it was the treated (time period after ear received any treatment), untreated ear (time period before ear received any treatment), or both ears (count of subjects in each treatment group). Ears will be presented by actual treatment group and overall as described in Section 3. Percentages for the treated ear summary will use the number of ears treated in the SfAS by treatment group as the denominator. Percentages for the untreated ear summary will use the number of ears not treated in the SfAS by treatment group as the denominator. Percentages for the both ear summary will use the number of subjects in the SfAS by treatment group as the denominator. In each classification of ear type (treated, untreated, both), if an ear has more than 1 AE within a system organ class, the ear will be counted only once in that system organ class. If an ear has more than 1 AE that codes to the same preferred term, the ear will be counted only once for that preferred term. For unqualified ears that receive study treatment in error, any ear-related AEs will be mapped to untreated or treated ear(s) based on when study drug administration occurred in the unqualified ear, as described in Section 8.1. Because an ear is deemed treated after receiving any study treatment as described in Section 3, it is possible for both ears to be deemed treated for ear-related TEAE analyses.

All AEs will be presented in data listings for subjects in the SfAS. A column will be included in the listings for whether the AE is treatment-emergent.

#### 8.4. Deaths, Serious Adverse Events, and Other Significant Adverse Events

Treatment-emergent SAEs, TEAEs leading to study withdrawal, and TEAEs resulting in death will be summarized separately for all subjects in the SfAS by treatment group and overall. All percentages will use the number of subjects in the SfAS by treatment group as the denominator. Summary tables will reflect a count and percentage of subjects experiencing at least 1 TEAE in each system organ class and preferred term within each AE subset (serious, leading to study withdrawal, death). In addition, the number of subjects experiencing any TEAEs in the respective subset will be reported. The tabular summary will be sorted by descending frequency of system organ class and preferred term based on the overall incidence.

Adverse events leading to study withdrawal, AEs resulting in death, and SAEs will be presented in data listings for subjects in the SfAS.

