### **8.4.4 Withdrawal of Subjects From Study Drug and/or Study Assessments**

Subjects may discontinue study drug or withdraw from the study for any of the following reasons:

- Adverse Event,

- Death,
- Lack of Efficacy,
- Lost to Follow-up,
- Non-Compliance with Study Drug,
- Other,
- Physician Decision,
- Pregnancy,
- Progressive Disease,
- Protocol Violation,
- Recovery,
- Study Terminated by Sponsor,
- Technical Problem,
- Withdrawal by Subject

Subjects are free to discontinue study drug and/or withdraw from the study at any time without providing reason(s) for withdrawal and without prejudice to further treatment. Subjects who discontinue study drug should be encouraged to continue to remain in the study and follow the per protocol assessments. Should a subject withdraw early from the study the reason(s) for study withdrawal will be documented in the electronic case report form (eCRF). All reasonable efforts will be made to have the subject return for one final assessment. Subjects withdrawing from the study will be encouraged to complete the same final evaluations as subjects completing the study according to this protocol, particularly safety evaluations. The aim is to record data in the same way as for subjects who completed the study.

Reasonable efforts will be made to contact subjects who are lost to follow-up. These efforts must be documented in the subject's file. Refer to Section 8.4.4 for details.

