## 9 DISCONTINUATION AND LOST TO FOLLOW-UP

### 9.1 Discontinuation of Study Intervention

Discontinuation from FX-322 does not mean discontinuation from the study, and remaining study procedures should be completed as indicated by the study protocol. If a clinically significant finding is identified (including, but not limited to changes from baseline) after enrollment, the investigator or qualified designee will determine if any change in participant management is needed. Any new clinically relevant finding will be reported as an adverse event (AE).

The data to be collected at the time of study intervention discontinuation will include the following:

- All efforts will be made for the subject to complete all of the follow up visits.
- If the subject does not wish to continue the follow up period, all efforts will be made for the subject to complete all assessments collected at the last follow up visit (see Section 8.4.4).

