### **Action Taken with Study Treatment in Response to Adverse Event**

The investigator will describe the action taken in the appropriate section of the eCRF, as follows:

- Dose Increased,
- Dose Not Changed,
- Dose Reduced,
- Drug Interrupted,
- Drug Withdrawn,

- Not Applicable,
- Unknown

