#### **14.1.7.1 Adverse Events**

The number and percentage of subjects reporting adverse events (AEs) will be summarized via the MedDRA system by organ class and preferred term. Data will be tabulated by severity, physician assessment of relationship to study drug, serious AEs, and AEs leading to death or study withdrawal. Adverse events of the ear will also be summarized by treated vs. non-treated ear.

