## 5. STUDY SUBJECTS

### 5.1. Disposition of Subjects

The disposition of all consented subjects will be summarized in tables by treatment group and overall per Section 3. Subjects who failed screening or were not randomized will only be included in the overall column. The following disposition information will be summarized:

- The number of subjects consented (signed Informed Consent).
- The number and percentage of subjects who failed screening and the reasons for failure (Did not meet criteria, Withdrew consent, Lost to follow-up, Other).
- The number of subjects not randomized versus randomized and the number and percentage of subjects for each randomization stratification factor (Etiology of

- hearing loss: Sudden sensorineural hearing loss (SSNHL), Noise-induced hearing loss (NIHL); Word Recognition Score at Screening:  $\geq 50\%$  correct,  $< 50\%$  correct).
- The number and percentage of subjects in each analysis set (FAS, PPAS, SfAS).
  - The number and percentage of subjects receiving study treatment at each treatment visit (Day 1, 8, 15, 21).
  - The number and percentage of subjects who completed the study through Visit 9 (Day 210).
  - The number and percentage of subjects who discontinued the study early and the reasons for withdrawal (Adverse Event, Death, Lack of Efficacy, Lost to Follow-up, Non-Compliance With Study Drug, Physician Decision, Pregnancy, Progressive Disease, Protocol Violation, Recovery, Study Terminated by Sponsor, Technical Problem, Withdrawal by Subject, Other).
  - The number and percentage of subjects who discontinued the study early for reasons related to COVID-19 (Subject has confirmed COVID-19, Subject decision, Site decision).

Percentages for the number of subjects who failed screening and the reasons for failure will be based on the number of subjects who signed informed consent. All other percentages will use the number of randomized subjects as the denominator. All rows will be summarized by randomized treatment group.

The number and percentage of subjects who attended each visit will be summarized by randomized treatment group for the FAS.

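### No planned table links adverse events to stopping or interrupting the injections, and the actual-dose safety columns move early stoppers out of the 4x group

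*SAP*

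**What the plan says.** **Which adverse event subsets are tabulated.** SAP 8.4: "Treatment-emergent SAEs, TEAEs leading to study withdrawal, and TEAEs resulting in death will be summarized separately for all subjects in the SfAS". The listings in that section have the same scope: "Adverse events leading to study withdrawal, AEs resulting in death, and SAEs will be presented in data listings for subjects in the SfAS". Protocol 14.1.7.1 agrees: "Data will be tabulated by severity, physician assessment of relationship to study drug, serious AEs, and AEs leading to death or study withdrawal".

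**Stopping drug versus leaving the study.** Protocol 9.1: "Discontinuation from FX-322 does not mean discontinuation from the study, and remaining study procedures should be completed as indicated by the study protocol". Protocol 8.4.4: "Subjects who discontinue study drug should be encouraged to continue to remain in the study and follow the per protocol assessments".

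**What is collected.** For each adverse event, Protocol 13 says: "The investigator will describe the action taken in the appropriate section of the eCRF". The options include Drug Interrupted and Drug Withdrawn.

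**Disposition and exposure.** SAP 5.1 gives reasons for leaving the study only: "The number and percentage of subjects who discontinued the study early and the reasons for withdrawal". It also counts subjects dosed at each of Days 1, 8, 15 and 21. SAP 8.2 tabulates by randomized group how many FX-322 doses (0 to 4) each subject received, and treatment at each visit in the qualifying ear. Neither section gives a cause for a missed injection.

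**Safety columns.** Under SAP 3 and 4, by-subject safety tables place each subject according to the number of FX-322 doses actually received in either ear. Subjects with three doses go to separate listings and to the total column.

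**The concern.** The second primary objective in both documents is the local and systemic safety of single and repeat doses. In a four-injection schedule, it bears directly on that objective whether adverse events keep subjects from completing the schedule. The protocol foresees the situation: Protocol 13 describes a decision on further dosing when subjects share the same event of special interest.

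The planned tables link adverse events to study withdrawal, while the protocol works to keep subjects who stop dosing in the study. The better that retention works, the fewer AE-caused stops appear in the study-withdrawal table. A report that followed SAP 8.4 exactly could say nothing, by group, about how often adverse events interrupted or ended the injections, although the data to say it had been collected.

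**Working it through.** The documents state no figure on this point, and the sample size of 24 per group has no formal basis, so there is nothing to reproduce. The check has three parts.

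**1. Trace one subject.** Take a subject who stops injections because of an adverse event and stays to Day 210.
- SAP 8.4, study-withdrawal table and listing: not included, because the subject did not withdraw.
- SAP 5.1, reasons for discontinuation: not included, for the same reason.
- SAP 5.1 and 8.2, dosing per visit: the missed injections show, without cause. Under Protocol 8.8.3 a missed injection is not made up and the subject returns for the next one, so the visit counts alone do not separate a single missed visit from a permanent stop.
- SAP 8.3, overall adverse event tables: the event is counted, but not its effect on dosing.
- SAP 8.3, listing of all adverse events: the event is listed. The SAP does not say whether action taken is shown.

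**2. Find the safety column.** FX-322 doses received, by randomized schedule and last injection given (no dosing errors):

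| Randomized | Stops after 1 | Stops after 2 | Stops after 3 | Completes 4 |
|---|---|---|---|---|
| 1x | 1 | 1 | 1 | 1 |
| 2x | 1 | 2 | 2 | 2 |
| 4x | 1 | 2 | 3 | 4 |
| Placebo | 0 | 0 | 0 | 0 |

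Two things follow.
- Only a subject randomized to 4x who received every injection has four FX-322 doses. A 4x subject who stops early moves to the 1x column, the 2x column, or the three-dose listing plus the total column. A 2x subject who stops after the first injection moves to 1x. A new table of events leading to stopping, laid out in the SAP 8.4 columns, would therefore read zero for 4x by construction.
- The 0-to-4 dose table in SAP 8.2 counts FX-322 only. Early stopping never changes the count in the 1x and placebo groups. In 2x it changes the count only for a stop after the first injection. Only in 4x is every early stop visible there. The per-visit counts do cover all four groups.

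**3. Illustrate the size.** Let p be the proportion of a group who stop because of an adverse event and stay in the study. The documents give no value; 2% to 15% is assumed. Expected number = 24 × p. Chance of at least one = 1 − (1 − p)^24.

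| p | Expected per group of 24 | Chance of at least one |
|---|---|---|
| 2% | 0.48 | 38% |
| 5% | 1.2 | 71% |
| 10% | 2.4 | 92% |
| 15% | 3.6 | 98% |

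Across 96 subjects the expected number runs from 96 × 0.02 = 1.9 to 96 × 0.15 = 14.4. None of these subjects belongs in the study-withdrawal table.

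**The case against.** The strongest reply is that little is hidden. The stated safety endpoints are adverse events, otoscopy and tympanometry, and all are tabulated. Perforation is shown by size and visit, and events of special interest have their own table and listing. Missed injections are counted by randomized group. This is an exploratory Phase 2a trial with descriptive safety, and SAP 1 allows supplementary analyses, labelled post hoc. All of that stands. It narrows the gap to the link between an event and a missed injection, but does not close it.

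Three stronger readings are tempting and are not supported.
- A reader might infer that the main tolerability result of the trial is missing. The documents name no main tolerability measure, and the events themselves are reported.
- A reader might set a true rate, say 2 of 24 (8.3%), against a planned table showing 0 of 24. A study-withdrawal table with no study withdrawals is correct; it does not estimate drug discontinuation. The denominator is also wrong for 4x. If 2 of 24 stopped early, with no other dosing deviations, that column would hold 24 − 2 = 22 subjects.
- A reader might infer that a full breakdown of reasons for missed injections is available at no cost. Action taken is recorded for each adverse event, but the documents do not show that other reasons for missing an injection are collected. Protocol 8.4.4 requires a documented reason for leaving the study.

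One limit remains. Under SAP 1, table and listing specifications are in separate documents, which were not available here. The gap in planned tables follows from the SAP text; whether the general adverse event listing shows action taken cannot be judged.

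**Conclusion.** The point holds as a reporting gap. No planned table connects adverse events with stopping or interrupting the injections, although the protocol separates that from study withdrawal and the eCRF records it. The actual-dose columns add to the problem: the 4x safety column keeps only subjects who completed all four injections. That statement assumes no dosing errors, such as an FX-322 injection given to a subject scheduled for placebo.

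The size is unknown. The range of 0.5 to 3.6 subjects per group rests wholly on the assumed 2% to 15% and only shows that a few subjects per group is plausible. No efficacy estimate, data collection or subject protection is affected. The change should still be made before unblinding, because it improves the answer to a primary objective at very small cost and would otherwise be labelled post hoc.

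**What to change.** - **SAP 8.4 and Protocol 14.1.7.1:** add a table and a listing of treatment-emergent adverse events whose eCRF action taken is Drug Withdrawn or Drug Interrupted. Present them by randomized group and overall, and state that this is an exception to the actual-dose columns of the Safety Analysis Set. Show the number of injections, FX-322 or placebo, received before onset.
- **SAP 5.1:** add a row for subjects who did not receive all four injections, split into those with such an event and all others. Do not split further by reason unless reasons are collected.
- Keep the study-withdrawal table as it is.

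The cost is SAP and protocol wording, one table, one listing and one disposition row. The event data come from an existing field and the row from dosing records already used in SAP 5.1 and 8.2; no visits or subjects are added. The drawback is that one safety table departs from the column rule used for the others, so it needs a clear footnote.

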##### 8.4.1. Adverse Events of Special Interest (AESI)

Protocol Section 13 defines adverse events of special interest.

AESIs will be summarized by treatment group and overall for all subjects in the SfAS. The summary will display the total number of AESIs as well as the count and percentage of subjects experiencing any AESI. The total number of AESIs and the count and percentage of subjects experiencing at least 1 AESI in each system organ class and preferred term will also be shown. All percentages will use the number of subjects in the SfAS by treatment group as the denominator. Therefore, if a subject has more than 1 AE within a system organ class, the subject will be counted only once in that system organ class. If a subject has more than 1 AE that codes to the same preferred term, the subject will be counted only once for that preferred term. The tabular summary will be sorted by descending frequency of system organ class and preferred term for overall incidence.

AESIs will be presented in a data listing for subjects in the SfAS.

#### 8.5. Clinical Laboratory Evaluation

Clinical laboratory evaluation data will be presented by laboratory parameter as descriptive statistics for the change from baseline to each visit and shifts from baseline to each visit by treatment group and overall for subjects in the SfAS. Unscheduled visit and early termination visit data will not be mapped to scheduled visits per Section 7.1.2. Unscheduled visit and early termination visit data will be excluded from summary tables and included in listings. The analyses for shifts from baseline to each visit will use laboratory-provided values of high (H), normal (N) or low (L) to classify laboratory results. Results that are reported as high panic (HP) or high normal (HN) will be classified as H, and results that are reported as low panic (LP) or low normal (LN) will be classified as L. Missing values will remain missing.

Pregnancy results will not be summarized, but will be included in listings with all other laboratory data for subjects in the SfAS.

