#### **10.1.10 Follow-up (Visit 9, [Day 210 +/- 15 days])**

The Follow-up Visit (Visit 9) will take place at Day 210 ( $\pm$  15 days). The following procedures will be performed at the Follow-up Visit:

- Record any AEs that have occurred since the last visit and any changes in concomitant medication.

- Perform otoscopy, standard pure tone audiometry, extended high frequency audiometry, word recognition testing, WIN testing, and tympanometry.
- Administer the Tinnitus Functional Index, C-SSRS, Hearing Handicap Inventory for Adults, and Hearing Screening Inventory.
- Collect blood sample for safety laboratory assessments.
- Collect blood sample for biomarker analysis.
- Record vital signs.

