#### **14.1.7.2 Clinical Laboratory Evaluations**

Clinical laboratory evaluations will be presented as summary statistics by treatment group for each timepoint as well as changes from baseline and/or shift tables. Pregnancy results will not be summarized but will be provided in line listings.

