## 2.4. Sample size

The sample size of approximately 24 subjects per group was considered adequate to explore the potential efficacy of FX-322 associated with various dosing schedules and was not based on formal statistical evaluation.

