## 8. SAFETY EVALUATION

### 8.1. Overview of Safety Analysis Methods

The assessment of local and systemic safety of single and repeated doses of FX-322 in subjects with stable sensorineural hearing loss is an objective of this study. The safety analyses will be performed for the safety analysis set and will include treatment-emergent adverse events (TEAEs), serious adverse events (SAEs), clinical laboratory measurements, vital signs, physical examination, otoscopic examination, tympanometry, concomitant medications, and Columbia-Suicide Severity Rating Scale (C-SSRS) assessments. Tabular summaries of descriptive statistics will be presented for all subjects included in the Safety Analysis Set and subjects will be classified into actual treatment groups based on the actual number of FX-322 doses received in any ear (qualified or not qualified).

Where appropriate, treated will be distinguished from the untreated ear, as described in Section 3. For unqualified ears that receive study treatment in error, the date and time of the study drug administration, or date if time is missing, or visit if date is missing (except for ear-related AEs, as provided below), will be used to identify assessments that will be classified as treated for safety analyses by ear.

If an assessment occurs on the same date that an unqualified ear receives study treatment in error, and assessment time or treatment start time is missing, the assessment will be presumed to have occurred prior to study drug administration for purposes of defining the ear as treated (i.e., the ear would be considered untreated at that assessment), with the exception of ear-related AEs, in which case the ear would be considered treated. The same logic would be applied to assessments other than ear-related AEs if the assessment occurred on the same visit that an unqualified ear receives study treatment in error and one or both dates are missing. For ear-related AEs, partial dates will be imputed for purposes of identifying treated ears in the same manner they are for purposes of defining TEAEs, as provided below.

For all safety endpoints, baseline will be the last non-missing value before first administration of study drug.

For all shift from baseline analyses, percentages will be based on the number of subjects in each baseline category.

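### SAP 8.5 sends results it labels high normal and low normal to High and Low in the laboratory shift table, so either the mapping or the label is wrong

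*SAP*

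**What the plan says.** SAP 8.5 plans two kinds of laboratory summary by parameter: descriptive statistics for change from baseline, and shifts from baseline. All laboratory data are also listed. For the shifts it uses "laboratory-provided values of high (H), normal (N) or low (L) to classify laboratory results". It then deals with four further flags. On the upper side: "Results that are reported as high panic (HP) or high normal (HN) will be classified as H". On the lower side: "results that are reported as low panic (LP) or low normal (LN) will be classified as L".

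SAP 8.1 fixes the denominators: "For all shift from baseline analyses, percentages will be based on the number of subjects in each baseline category". It also sets the safety baseline as the last non-missing value before the first dose, which on the planned schedule is the Screening sample.

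The protocol foresees the tables but gives no flag mapping. Section 14.1.7.2 says: "Clinical laboratory evaluations will be presented as summary statistics by treatment group for each timepoint as well as changes from baseline and/or shift tables". The only scheduled post-baseline draw is at Visit 9, Day 210 (Protocol 10.1.10: "Collect blood sample for safety laboratory assessments"). SAP 8.5 keeps unscheduled and early-termination laboratory results out of the summary tables.

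**The concern.** A shift table is read for movement across the limits of the normal range. Here two flags whose names contain the word normal are grouped with the panic values and placed outside the Normal category. Taken at its word, the rule errs in both directions. It can show a shift to High when both results are labelled normal, and it can conceal a move from a result labelled normal to one that is high or at panic level.

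Systemic safety is part of the second primary objective (Protocol 7.1). Safety laboratories are scheduled only at Screening and Day 210, so no intermediate scheduled visit exists against which a misplaced result could be seen. The arms are small: 24 are planned per group, so one subject is 1/24 = 4.2 percentage points of an arm. The share is larger within a baseline row that holds fewer than 24.

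**Working it through.** The plan states no figure to reproduce. The sample size itself "was not based on formal statistical evaluation", so power, alpha and effect size play no part. The check is a flag-by-flag reading of SAP 8.5, followed by a search for any definition or override elsewhere.

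**1. The two mappings side by side**

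| Category | As SAP 8.5 is written | As the flag names read |
|---|---|---|
| High | HP, H, HN | HP, H |
| Normal | N | HN, N, LN |
| Low | LN, L, LP | L, LP |

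**2. What happens to individual changes (baseline to Day 210)**

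| Change in flag | Cell as written | Cell by flag name |
|---|---|---|
| N to HN | Normal to High | Normal to Normal |
| HN to N | High to Normal | Normal to Normal |
| HN to H or HP | High to High | Normal to High |
| H to HN | High to High | High to Normal |
| LN to HN | Low to High | Normal to Normal |

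The mirror-image changes on the lower side behave in the same way.

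**3. Net effect on the Normal-to-High cell.** For one analyte in one arm, let
- a = subjects going from N to HN,
- b = subjects going from N to H or HP,
- c = subjects going from HN to H or HP,
- d = subjects going from LN to H or HP.

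Count as written: a + b. Count by flag name: b + c + d. The difference is a − c − d, which can have either sign.

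The percentages move as well. The Normal row has denominator n(N) as written and n(N) + n(HN) + n(LN) by flag name, where n is the number of subjects with that flag at baseline. Numerator and denominator both change, so the direction of the percentage cannot be fixed either.

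**4. Size, as an illustration only.** Neither document gives a frequency for HN or LN. Assume that 1% to 5% of results carry one of these flags:
- per arm of 24: 0.01 × 24 = 0.24, and 0.05 × 24 = 1.2 subjects per analyte per visit;
- over all 96 planned subjects: 0.01 × 96 = 0.96, and 0.05 × 96 = 4.8.

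The per-arm figures are the relevant ones, because the tables are presented by treatment group as well as overall. If the laboratory never issues these flags, the effect is zero.

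**5. Search for a definition or override.** HN and LN are not in the SAP abbreviation list. Protocol 14.1.7.2 gives no mapping. SAP 8.1 sets general safety rules but does not mention the flags. SAP 11 declares one change from the protocol, on multiplicity. Nothing in either document resolves the conflict.

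**6. Reach.** The change-from-baseline statistics and the listings do not use the mapping. No efficacy analysis uses it. Laboratory tables are not among the interim outputs in SAP 10.

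**The case against.** The strongest reply is that the meaning of a laboratory-provided flag is set by the laboratory's own dictionary, which is not in the documents. The SAP lists N separately and pairs HN with HP and LN with LP. That is compatible with HN and LN being out-of-range, non-panic flags that were spelled out wrongly in the text. In that case the mapping is right, and recoding HN and LN to Normal would hide real abnormal results. This stands, and it decides the order of the remedy. It does not clear the text: if the mapping is right, the label is wrong. Plain H and L also already exist for out-of-range results, so this reading needs the laboratory's confirmation.

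A reader might infer three stronger things that the documents do not support:

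- That normal results will certainly be counted as abnormal. This follows only if the flags mean what the SAP calls them.
- That shifts from Normal to High or Low are inflated. The difference a − c − d has no determined sign, and the denominators change too. The same mapping applies in every arm, and nothing shows a differential effect between arms.
- That this table is the main laboratory safety output. SAP 8.5 also plans change-from-baseline statistics and full listings. Abnormal laboratory findings can be reported as adverse events under Protocol 13, and laboratory results are not among the safety endpoints named in Protocol 7.2.

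**Conclusion.** The point holds as an internal contradiction in SAP 8.5. Read literally, the rule puts results that the SAP calls normal in the High and Low categories, misplaces some shifts in both directions, and alters the baseline-category denominators. Either the mapping or the wording must change, whichever meaning the laboratory gives the flags.

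The consequence is confined to the categorical laboratory shift tables from Screening to Day 210. Direction and size are unknown. The range of about 0.2 to 1.2 subjects per arm per analyte per visit rests wholly on an assumed flag frequency of 1% to 5% and on the planned 24 per arm. Severity is low.

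**What to change.** Before database lock, in this order:

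1. Obtain the definitions of HN and LN from the laboratory transfer specification.
2. If they are within-range flags, as the SAP's words say, amend SAP 8.5 so that H and HP are High, L and LP are Low, and N, HN and LN are Normal.
3. If they are out-of-range, non-panic flags, keep the mapping and correct the labels in the text.
4. In either case, add the flags to the abbreviation list.

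The cost is one query to the laboratory, one sentence in the SAP and at most one line of mapping code. No listed interim table changes. If the correction falls after the interim unblinding, the blinded team should make and date it, in keeping with the separation that SAP 10 already sets out.
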